Clinical and Radiographic Evaluation of MTA versus Biodentine as Pulpotomy Agents in Immature First Permanent Molars: A Randomized Clinical Trial

Protocol submitted to the Faculty of Dentistry, Cairo University
by
[name]
Associate Professor of Pediatric Dentistry

Faculty of Dentistry
Cairo University
18 Jan 2017

I. Administrative information:

1. Title:

Clinical and Radiographic Evaluation of MTA versus Biodentine as Pulpotomy Agents in Immature First Permanent Molars: A Randomized Clinical Trial

2. Protocol Registration:

To be registered on Clinicaltrial.gov

3. Protocol version:

Final version.

4. Funding:

This trial is self-funded.

5. Roles and responsibilities:

1. **[name] ([name])** Associate Professor of Pediatric Dentistry, Cairo University. Responsible for the clinical part of study, and Data monitoring.
2. **[name] ([name])** Professor of Pediatric Dentistry, National University of Singapore, responsible for the writing revision and proof reading.
3. **[name] ([name])** Associate Professor of Pediatric Dentistry, Misr University for sciences and technology. Responsible for the clinical evaluation of the cases at the evaluation intervals

II. Introduction

6-background and rationale:

Description of research question:

P: children with cariously exposed immature mandibular first permanent molars

I: Pulpotomy using Biodentine

C: MTA pulpotomy

O:

	Outcome	Tool/Device	Unit
Primary Outcome	spontaneous pain, sensitivity to percussion/palpation)	Pain questionnaire	Binary
	Swelling or sinus tract	Visual examination by the third author	Binary
	Mobility	Back of the mirror	Binary
Secondary outcome	Stage of root development	Standardized periapical	3 stages
	Crown: Root ratio	Standardized periapical	2:1 ≥2:1
	Apex	Standardized periapical	Blunder apex, partially open, constricted
	Presence of radiolucency	Standardized periapical	Binary

S: Randomized clinical trial

T: 18 months (Baseline, 6, 12 and 18 months)

Research question: is Biodentine used as pulpotomy material in cariously exposed immature mandibular first permanent molars more successful clinically and radiographically than MTA pulpotomy?

Justification for undertaking the trial:

Dental caries and its tremendous effects are considered one of the greatest challenges to the integrity of the developing dentition. Although the debates exist regarding the success rate of vital pulp therapy in cariously-exposed pulps, the technique is recommended to be performed on immature teeth [1,2].

Carious exposures in young permanent molars may cause irreversible damage to the pulp tissue and arrest root development, which can jeopardize the long-term tooth retention [3]. Hence, the main objective of treating carious-exposed immature teeth is to

maintain pulp vitality and enhance continuation of root development and apical closure. This approach is called apexogenesis. [4]

Vital pulp therapies should provide a biologically conductive environment for the pulp tissue to regenerate and prevent future bacterial contamination by using an appropriate pulp-capping agent. [3] The pulp capping material should possess biocompatibility, bactericidal effect, ensure a biologic seal, and induce hard tissue formation. [3,5]

A new era of regenerative endodontics recommended Mineral trioxide aggregate (MTA), to be considered the new gold standard for vital pulp therapies, that provides long-term seal, acceptable biocompatibility [6], and dentinal bridge formation as reported by various animal and human studies. [7,8] When the role of Calcium hydroxide (CH), that has been the most commonly used material for vital pulp therapy for many decades, was diminished, [9] claims raised against its use. The claims were attributed to several disadvantages including the exitance of tunnel defects in induced dentinal bridges, poor adherence to dentine, and lack of long-term seal. [10]

MTA is a powder that consists of fine hydrophilic particles that set in the presence of moisture. The setting time of MTA in moisture is less than 4h. MTA consists of tricalcium silicate, tricalcium aluminate, tricalcium oxide and silicate oxide. [11] MTA was considered a remarkable biocompatible material with various clinical applications that include surgical and non-surgical applications such as pulp capping [12], furcation and Perforation repairs [13], apexification and root end fillings [11,14]. Although the high clinical success of MTA material, there were always Issues prevented the clinicians to use it for many cases. The main reasons were related to very long setting time and difficult manipulation. [15]

Biodentine new bioactive calcium silicate-based cement has been recently launched in the dental market as a 'dentin substitute'. This new biologically active material facilitates its penetration through opened dentinal tubules to crystallize interlocking with dentin and provide mechanical properties. Biodentine has been developed using MTA based cement technology and hence; added improved properties such as physical qualities and handling, and its wide range of recommended applications in endodontic repair and pulp capping. [16]

Radiographic imaging of the dentoalveolar complex has been assessed using conventional periapical radiography, the benchmark for intraoral radiographic imaging for decades. Their known limitations of image magnification, distortion, superimposition and overlap of anatomy always led to unclear and misrepresentation of structures. Although the advent of digital intraoral radiography didn't improve these limitations, it provided a more active image manipulation than the film-based radiographs and reduced patient exposure

substantially. [17, 18]

7 - Objectives and hypothesis:

The objective of this prospective randomized clinical trial is to compare the clinical / radiographic outcomes of MTA and Biodentine as pulpotomy biomaterials used in apexogenesis treatment of symptomatic / asymptomatic vital immature mandibular permanent first molars with carious pulp exposure.

8-Trial Design:

Randomized clinical trial (RCT), parallel groups with 1:1 allocation ratio, Triple blinded (patient, clinical and radiographic assessor of the results and statistician)

III- Methods:

9-Study settings:

This study will be carried out on patients attending the outpatient clinic in Pediatric Dentistry department, Faculty of Dentistry, Cairo University, Egypt. the procedures will be carried out by [name] Associate Professor of Pediatric Dentistry in Pediatric Dentistry clinic. expected time duration from 2017 to 2018.

10- Eligibility criteria:

Inclusion criteria:

- Medically free children.
- Bilaterally Symptomatic / asymptomatic vital immature mandibular first permanent molars (with clinical carious exposure of the pulp and presence of bleeding upon exposure)
- Patients with an age range from 7-8 years.
- Absence of sinus tract, soft tissue swelling.

The exclusion criteria:

- Molars were excluded if non-restorable.
- excessive mobility (more than 1 mm horizontally).
- Radiographic evidence of peri- and /or inter-radicular lesions, internal/ external root resorption, pulp/ canal calcifications.

IV- Intervention:

Diagnosis:

1. Full history data will be collected, including personal, medical and previous dental data
2. Clinical examination using mirror and probe to assess the inclusion criteria.
3. Radiographic examination using preoperative digital periapical radiograph to assess the inclusion criteria.
4. Preoperative photograph will be taken.

Operative procedure:

Experimental group:

1. Injection of local anesthesia and rubber dam isolation.
2. caries and roof of the pulp chamber will be removed by a fissure diamond bur (Diatech, Heerbrug, Switzerland) and high-speed handpiece with coolant.
3. The pulps will be amputated to the orifice level using a long-shank diamond round bur.
4. Haemostasis will be achieved by gentle placement of a saline-moistened cotton pellet over amputated pulps for 5–10 min.
5. Calcium silicate-based BiodentineTM (Septodont Ltd., Saint Maur des Fausse's, France) will be mixed according to the manufacturer's instructions, radicular pulp will be covered by the material using a wet cotton pellet.
6. A self-cure glass ionomer (GC; GC Corporation, Tokyo, Japan) will be placed over the pulpotomy agent as a final restoration.
7. Immediate post-operative radiograph and photograph will be taken.

Control group:

The same procedures will be carried out as the experimental group, but the pulp stumps will be covered with fast-setting mineral trioxide aggregate (MTA) ENDOCEM MTA (Maruchi, Wonju, Korea) and will be prepared according to the manufacturer's instructions. A 3-mm-thick layer of MTA will be placed over the amputated pulps and will be gently adapted to the dentinal walls using a wet cotton pellet. A self-cure glass ionomer (GC; GC Corporation, Tokyo, Japan) will be placed over the pulpotomy agent as a final restoration.

Postoperative care:

Instructions to avoid lip and cheek biting in addition to oral hygiene measures.

Follow up:

Assess the outcomes clinically and radiographically at (baseline, 6, 12 and 18 months).

Criteria for discontinuing or modifying intervention:

In case of an unsuccessful outcome after pulpotomy, the molars will be managed by other pulp therapy techniques or extraction.

Strategies to improve adherence to intervention:

Explanation to the parents about the importance of follow up visits in addition to treatment of other dental problems.

Concomitant care:

None needed.

12- Outcomes:

	Outcome	Tool/Device	Unit
Primary Outcome	spontaneous pain, sensitivity to percussion/ palpation)	Pain questionnaire	Binary
	Swelling or sinus tract	Visual examination by the third author	Binary
	Mobility	Back of the mirror	Binary
Secondary outcome	Stage of root development	Standardized periapical	3 stages
	Crown: Root ratio	Standardized periapical	2:1 ≥2:1
	Apex	Standardized periapical	Blunder apex, partially open, constricted
	Presence of radiolucency	Standardized periapical	Binary

Primary outcome:

Clinical assessment of the findings in the table will be conducted at follow up intervals (baseline, 6, 12 and 18 months)

Secondary outcome:

Radiographic assessment of stage of root development, crown: root ratio, apical closure and presence of radiolucency will be conducted through digital periapical radiographs by parallel

technique using film holders. The assessments will be carried out at follow up intervals (baseline, 6, 12 and 18 months)

13- Participants timeline:

	Study period				
	Enrolment	Allocation	Post allocation		Close out
Time point	For 7 months	0	6 months	12 months	18 months
Enrolment:					
Eligibility screen	✓				
Informed consent	✓				
History taking	✓				
Clinical examination	✓				
Preoperative radiograph	✓				
Allocation		✓			
Interventions:					
Access preparation		✓			
Placement of Biodentine (experimental group)		✓			
Placement of MTA (Control group)		✓			
Final restoration		✓			
Assessment					
Periapical radiograph as baseline reference			✓	✓	✓

Clinical examination to assess pain, swelling, fistula, tooth mobility			✓	✓	✓
Periapical radiograph to assess stage of root development, crown: root ratio, apical closure and presence of radiolucency			✓	✓	✓

14- Sample size calculation:

Sample size is calculated based upon the results of Alqaderi et al (2014) [15] who reported clinical success rate (primary outcome) for MTA = 90%. Since no relevant literature reported the clinical success rate of Biodentine in permanent teeth of pediatric patients, the success rate was assumed to be 50%. Using alpha level = 0.05 and β level = 0.20 (80% Power); the minimum estimated sample size will be 20 subjects per group for a total of 40 subjects. To compensate for a drop-out rate of 15%, the number is increased to 23 subjects per group for a total of 46 subjects.

Sample size calculation was performed using IBM® SPSS® Sample Power® Release 3.0.1.

15- Recruitment:

All patients attending the outpatient clinic in pediatric dentistry department complaining from carious mandibular first permanent molars will be screened and enrolled in the study if they meet the eligibility criteria.

16- Allocation:

Sequence generation:

Access cavity prepared molars will be assigned into experimental or control group using simple randomization 1:1 by the help of the computer software(random.org).

Allocation concealment mechanism:

Numbered opaque sealed envelopes.

Implementation:

The child will choose an envelope randomly and open it after caries removal so that the operator knows which pulpotomy agent will be used only after finishing the access cavity. Sequence generation will be done by the third author and the patient assignment will be done by the operator.

17- Blinding:

Patients and their parents, the assessor and the statistician will be blinded.

18- Data collection methods:**Primary outcome:**

Clinical assessment of the following findings:

1. postoperative pain: through asking the child and the parent if there is pain either continuous or intermittent
2. Swelling: through visual examination by the assessor either intraorally or extra-orally.
3. Sinus or fistula through visual examination of the gingiva by the assessor.
4. Tooth mobility: By the back of the mirror checked by the assessor to detect mobility in any direction

This assessment will be conducted every follow-up visit throughout the study period at baseline, 6, 12 and 18 months.

Secondary outcome

Radiographic assessment to detect stage of root development, crown: root ratio, apical closure and presence of radiolucency through standardized periapical radiograph by parallel technique using film holder. This assessment will be conducted every follow-up visit throughout the study period at baseline, 6, 12 and 18 months.

Postoperative records will be performed by the assessor to avoid individual variability and to promote data quality.

19- Data management:

Explanation to the parents about the importance of the follow-up visits in addition to treatment of other dental problems are plans to promotes participants retention and complete the follow-up. Also, phone calls before the dates before the next follow-up visit will be scheduled.

All findings will be documented in the examination sheet then transferred electronically to computer in secured lace sequentially.

20- statistical methods:

All data will be collected, checked, revised, tabulated and entered into the computer. Qualitative data will be presented as frequencies and percentages. Since the study is a split-

mouth design; Wilcoxon signed-rank test will be used to compare between the two groups. Friedman's test will be used to study the changes by time within each group. Kaplan-Meier survival curve will be constructed to calculate the mean survival estimates of the two groups. Comparison between survival times will be performed using Log rank test.

The significance level will be set at $P \leq 0.05$. Statistical analysis will be performed with IBM® SPSS® Statistics Version 20 for Windows.

21-Monitoring:

The study data and results will be monitored regularly by the assessor who will have full access to these data.

22- Harms:

No reported adverse effects for both testing pulpotomy agents. Any adverse events appear during the trial will be recorded, documented and treated.

23-Auditing:

Auditing of the study design will be done by the evidence-based committee, Faculty of Dentistry -Cairo University.

V- Ethics and dissemination:

24-Research ethics approval:

This protocol and the template informed consent form will be reviewed by the Ethics Committee of Scientific Research - Faculty of Oral and Dental Medicine - Cairo University.

25-Protocol amendments:

Any modification to the protocol which may have an impact on the conduction of the study, potential benefit of the patient or my affect patient safety including, the changes of study objectives, study design, sample size or significant administrative aspects will require a formal amendment to the protocol.

26-Consent and Assent:

Researcher will discuss the trial with legal guardian of each participating child. They will be able to have an informed discussion with the researcher after explaining the procedure in simple words. Verbal assent will be taken orally from the participating child while written consent will be taken from the legal guardian of each participating child who is willing to participate in the

® IBM Corporation, NY, USA.

® SPSS, Inc., an IBM Company.

trial. All consent forms will be translated into Arabic.

27-confidentiality:

All study related information will be stored securely. All participants information will be stored in locked file cabinets in an area with limited access. Process and administrative forms will be identified by a coded ID (identification number) only to maintain participants confidentiality. All records that contain names or other personal identifiers will be stored separately from study records identified by code number

28-Declaration of interests:

Non-financial.

29- Access to data:

All principal investigators will be given access to the data sets. All data sets will be password protected. To ensure confidentiality, data dispersed to study team members will be blinded of any identifying participants information.

30-Ancillary and post-trial care:

Full mouth treatment will be offered to all participating children in addition to postoperative care and preventive measures through regular follow up visits after the end trial.

31- Dissemination policy:

-Study results and articles will be published in related journal.

References:

3. Witherspoon D. Vital pulp therapy with new materials: new directions and treatment perspectives permanent teeth. J Endod 2008; 34: S25–S28.

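### The clinical success rate that sets the sample size is never defined or dated, and no primary test, survival event or multiplicity rule is named

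*Combined protocol and SAP*

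**What the plan says.** Section 14 takes its control rate from a cited study "who reported clinical success rate (primary outcome) for MTA = 90"%, assumes 50% for Biodentine, and reaches 20 subjects per group (40 in total) at alpha 0.05 and 80% power, raised to 23 per group for drop-out. This is one binary variable. The section gives it no definition and no visit.

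Section 12, like the outcome table in Section 6, puts three binary rows under the primary outcome: pain with sensitivity ("spontaneous pain, sensitivity to percussion/palpation" in Section 6), swelling or sinus tract, and mobility. It adds: "Clinical assessment of the findings in the table will be conducted at follow up intervals (baseline, 6, 12 and 18 months". Section 6 gives the time frame as "T: 18 months (Baseline, 6, 12 and 18 months". Section 13 describes the visit as "Clinical examination to assess pain, swelling, fistula, tooth mobility" and ticks it at 6, 12 and 18 months only. Section 18 lists four items (pain by asking child and parent, swelling, sinus or fistula, mobility) at baseline and each follow-up visit, and does not mention percussion or palpation.

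Section 20 says "Wilcoxon signed-rank test will be used to compare between the two groups", adds Friedman's test within groups and Kaplan-Meier curves, and says "Comparison between survival times will be performed using Log rank test". "The significance level will be set at" P ≤ 0.05. No test is attached to an outcome or a visit.

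Section IV (criteria for discontinuing or modifying intervention) sends molars with an unsuccessful outcome to other pulp therapy or extraction. It does not define unsuccessful or say how such a molar is scored afterwards.

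**The concern.** The power statement belongs to one variable tested once. The outcome and analysis sections offer several candidates (three rows, three follow-up visits, a paired rank test and a log-rank test) and do not say which one carries the trial's conclusion. Three things follow.

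- **Choice after the fact.** The finding, visit or test reported as primary could be selected once results are known, and no multiplicity rule limits this.
- **Power without an owner.** The 80% applies to a success variable at the assumed rates. A single sign that captures only some of the failures would have lower power, and the plan gives no rates for single signs.
- **Scoring gaps.** A molar that fails at 6 months, is retreated and is symptom-free at 18 months could be scored a success. An extracted molar could be treated as missing. Mobility is recorded as present or absent in any direction, while Section 10 excludes only horizontal mobility above 1 mm. A molar could therefore carry the mobility finding from entry.

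**Working it through.** **1. Reproduce the plan's figure.** Inputs from Section 14: p1 = 0.90, p2 = 0.50, alpha 0.05 (two-sided assumed, as sidedness is not stated), power 0.80. With pooled proportion 0.70:

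n = [1.960·√(2·0.70·0.30) + 0.842·√(0.90·0.10 + 0.50·0.50)]² / 0.40² = (1.270 + 0.491)² / 0.16 = 19.4, so 20 per group.

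The stated 20 is reproduced for one binary endpoint, two independent groups, tested once. The normal-approximation power at 20 is 0.813.

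**2. Power of one composite, two groups of 20.** Exact binomial enumeration over all outcomes, failure 10% against 50%: Pearson chi-square 0.838, Fisher 0.742. Fisher first reaches 80% at 23 evaluable per group (0.811; 22 gives 0.786).

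**3. The same composite if the design is split-mouth.** Section 8 says parallel groups; Section 20 says split-mouth. For within-child correlation ρ (assumed 0 to 0.2), the probability that both molars fail is 0.10·0.50 + ρ·√(0.10·0.90·0.50·0.50) = 0.05 + 0.15ρ. The probabilities that only the MTA molar or only the Biodentine molar fails are therefore 0.05 and 0.45 (ρ = 0), 0.035 and 0.435 (ρ = 0.1), 0.02 and 0.42 (ρ = 0.2). On binary data the signed-rank test is the asymptotic McNemar test, z = (b − c)/√(b + c), where b and c are the two discordant counts. The documents do not settle whether there would be 20 pairs (20 molars per arm) or 40 (40 children, each with both molars, since Section 10 requires bilateral involvement).

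| Pairs | Asymptotic McNemar, ρ = 0 / 0.1 / 0.2 | Exact McNemar, ρ = 0 / 0.1 / 0.2 |
|---|---|---|
| 20 | 0.790 / 0.837 / 0.892 | 0.694 / 0.740 / 0.792 |
| 40 | 0.985 / 0.992 / 0.997 | 0.973 / 0.985 / 0.994 |

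**4. Multiplicity, as illustration only.** If all three rows were tested at all three follow-up visits at 0.05 and the tests were independent, the chance of at least one false positive would be 1 − 0.95⁹ = 0.370. For three rows at one visit it is 1 − 0.95³ = 0.143. Both are ceilings; rare or correlated findings bring them down.

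**5. Type I error of the chi-square test at 20 per group.** Enumerated over common failure rates of 2% to 98% in steps of 2%, the largest value is 0.053.

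**The case against.** The best defence is that Section 14 itself calls the clinical success rate the primary outcome. The three rows then read as components of one composite. A log-rank test also needs a single failure event, and 18 months is the natural visit. On this reading the plan has one endpoint and merely leaves out its definition. The intent is plausible and should be granted. It still does not fix the components, the visit, the survival event or the primary test.

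A reader might go further and infer that the plan commits to nine uncorrected primary tests, none of them the powered variable, with a 37% false-positive risk. The documents do not support that. Section 20 assigns no test to any row or visit, so the count of nine is a construction and the 37% is a ceiling.

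A reader might also infer that a split-mouth trial would fall short of 80% power. That holds only for 20 pairs with exact tests, or with an asymptotic test when pairs are uncorrelated (79%). With 40 pairs, power is 97% or more.

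Nor is baseline scoring a general problem. Swelling and sinus tract are absent at entry by eligibility, Section 18 asks about postoperative pain, and Section 13 ticks the outcome examination only after treatment. Mobility up to 1 mm at entry is the real gap, and a small one. Section 13's pain could be shorthand that includes percussion and palpation; the omission is clearer in Section 18.

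**Conclusion.** The point stands as an ambiguity that matters, and not as proof that the sample size is wrong. Twenty per group is right for one binary success variable tested once at two-sided 0.05, with 84% power by chi-square or 74% by Fisher at the plan's own rates. The plan does not define that variable, date it or name its test, so the stated 80% belongs to no specified analysis. The primary finding or visit is open to choice after the data are seen, and a retreated molar could count as a success. The split-mouth figures rest on an assumed correlation of 0 to 0.2 and on a number of pairs that the documents leave open: 79–89% asymptotic and 69–79% exact for 20 pairs, 98–99.7% and 97–99% for 40. The multiplicity figure rests on assumed independence and on every row and visit being tested.

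**What to change.** **Endpoint.** Name one primary endpoint: cumulative clinical success through 18 months. A molar succeeds if none of the Section 12 clinical findings is recorded at 6, 12 or 18 months and it has had no further pulp treatment or extraction for any pulpal or periapical reason, including a radiographic one. This is a scoring rule only and leaves management unchanged.

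**Survival analysis.** Use the same failure event for Kaplan-Meier and log-rank, dated to the visit where it is first recorded. Censor molars lost without an event at their last visit.

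**Drop-outs.** For the 18-month comparison, analyse molars with a known outcome and add a sensitivity analysis counting drop-outs as failures.

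**Baseline.** Findings at baseline are not events. Record mobility grade at each visit and count mobility only if new or increased from baseline.

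**Test.** Test the endpoint once at two-sided 0.05 with a 95% confidence interval. Once Sections 8 and 20 are reconciled, use Pearson chi-square if parallel or McNemar if split-mouth. Restate the power for that test and that number of molars or pairs.

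**Everything else.** Make single findings, the 6- and 12-month results, and the log-rank and Friedman tests secondary. Reconcile Sections 12, 13 and 18 on percussion and palpation.

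**Cost.** Wording in Sections 12, 13, 14, 18 and 20, and one extra recorded item (mobility grade). Results on a single sign or an early visit can no longer be claimed as primary. A transient finding counts as failure. Chi-square can slightly exceed its nominal level (about 0.053 at worst). The stated power may change; if Fisher's test were preferred, 80% would need 23 evaluable molars per group before drop-out.

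### Simple randomisation of molars fits neither stated design: it does not give each child one molar per material (split-mouth), and it secures neither 23 per group nor balance on pre-operative symptoms (parallel)

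*Combined protocol and SAP*

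**What the plan says.** All references are to the combined protocol and SAP.

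- **Allocation (Section 16, Sequence generation):** "Access cavity prepared molars will be assigned into experimental or control group using simple randomization 1:1". The unit is the molar. No blocks, strata, minimisation or rule linking a child's two molars is given. Under Implementation, "The child will choose an envelope randomly and open it after caries removal".
- **Design (Section 8):** "Randomized clinical trial (RCT), parallel groups with 1:1 allocation ratio".
- **Design (Section 20):** the study is called split-mouth. The sentence giving this as the reason for a paired test ends "mouth design; Wilcoxon signed-rank test will be used to compare between the two groups". The other methods are Friedman's test, Kaplan-Meier curves and a log-rank test. No covariate, stratified test or subgroup is named.
- **Population (Sections 7 and 10):** the objective covers "symptomatic / asymptomatic vital immature mandibular permanent first molars with carious pulp exposure", and entry requires "Bilaterally Symptomatic / asymptomatic vital immature mandibular first permanent molars".
- **Sample size (Section 14):** 20 per group is the minimum. For drop-out, "the number is increased to 23 subjects per group for a total of 46 subjects". This section counts subjects; Section 16 randomises molars.

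**The concern.** The allocation rule has to produce the data structure that the analysis needs. A signed-rank comparison of the materials needs one molar on each material in every child. A parallel comparison with 23 per group needs something that holds the arm sizes. Unrestricted randomisation of molars provides neither.

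A baseline factor is also left uncontrolled. The trial enrols both symptomatic and asymptomatic pulps, and the first component of its primary outcome is spontaneous pain and sensitivity. Pre-operative symptoms are therefore close in kind to the outcome. History and clinical examination come before allocation, so the factor could be used for stratification. As planned, neither the allocation nor the analysis uses it.

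**Working it through.** **1. The plan's own sample size.** Inputs from Section 14: 90% and 50% success, alpha 0.05 (taken as two-sided), 80% power. The pooled-variance formula with mean proportion 0.70 is

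n = [1.96 × √(2 × 0.70 × 0.30) + 0.842 × √(0.90 × 0.10 + 0.50 × 0.50)]² / 0.40² = (1.270 + 0.491)² / 0.16 ≈ 19.4, so 20 per group.

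This matches the plan. Its 23 is 20 × 1.15; dividing by 0.85 gives 23.5, so 24. The calculation is for two independent groups.

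**2. Split-mouth reading.** If a child's two molars are randomised independently at 1:1, P(same material on both) = 0.5² + 0.5² = 0.5.
- If 46 counts molars: 23 children, of whom 23 × 0.5 = 11.5 are expected to give no pair. The 95% range of usable pairs is 7 to 16.
- If 46 counts children: 46 × 0.5 = 23 are expected to give no pair.

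**3. Parallel reading, arm sizes.** Treat 46 as independently randomised units, so the size of one arm is Binomial(46, 0.5).
- P(exactly 23:23) = C(46, 23) / 2⁴⁶ = 11.7%.
- P(smaller arm is 19 or fewer) = 2 × P(X ≤ 19) = 30.2%.

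Power with all 46 evaluable, for 90% against 50%:

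| Split | Power |
|---|---|
| 23:23 | 86.7% |
| 18:28 | 84.3% to 86.0% |
| 16:30 | 82.1% to 85.0% |
| Averaged over simple randomisation | 86.0% |

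The ranges depend on which material has the smaller arm. The mean loss is 86.7 − 86.0 = 0.7 points.

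**4. Parallel reading, symptom status.** The documents do not give the share of symptomatic molars, so 30% to 50% is assumed. Exact enumeration of simple randomisation of 46 units gives:

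| Symptomatic molars | P(arms differ by ≥ 10 points) | P(≥ 20 points) |
|---|---|---|
| 14 of 46 | 47.0% | 16.1% |
| 23 of 46 | 46.5% | 18.6% |

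A share of 70% (32 of 46) gives the same figures as 14 of 46.

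**5. What such an imbalance does.** The shift in the observed difference is the imbalance times the effect of symptoms on success. That effect is not in the documents either.
- Assumed 20-point effect: 0.20 × 0.20 = 4 points.
- Assumed 40-point effect: 0.20 × 0.40 = 8 points.

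The planned difference is 40 points. Four scenarios with no material effect, assumed symptom effects of 20 to 40 points and an unadjusted two-proportion test were simulated (100,000 runs each). The mean difference was about 0 and the overall type I error 4.2% to 5.1%. Among allocations with at least 20 points of imbalance, the type I error was 6.6% to 10.7%.

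**The case against.** The strongest reply is that the real defect is the contradiction between parallel and split-mouth, and that everything here follows from it. If each child received one material per side, the arms would be equal by construction and child-level factors would cancel. The bilateral criterion can even be read as requiring both molars to share a symptom status, which would leave nothing to imbalance. This is right about the order of repair. It does not rescue Section 16, which nowhere says that the second molar receives the other material. The one-half figure does assume independent randomisation of a child's two molars, which is the literal reading of the text but is not spelled out.

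Second, the envelopes may be a prepared set of 23 and 23. Drawing without replacement would then give exactly 23:23, and the arm-size probabilities would not apply. The text does not settle this. Such a set would still not balance symptom status or create pairs.

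Third, a reader might infer that any difference found between the materials could simply be a difference in pulps, or that the result is biased. The documents do not support that. Chance imbalance is not systematic: the expected difference is unaffected and overall type I error stays near 5%. Neither the share of symptomatic molars nor their prognosis is given, and the assumed shifts of 4 to 8 points are well below 40. The 40-point difference is not a firm yardstick, however, because it rests on a Biodentine rate that Section 14 assumes for lack of literature.

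Fourth, a reader might take the 30.2% chance of an arm below 20 as a 30% chance of an underpowered trial. It is not. Twenty per group is the requirement under equal allocation, and 46 evaluable units split 16:30 still have 82.1% to 85.0% power.

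**Conclusion.** The point holds in a conditional form. As written, the allocation rule matches neither stated design.

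- **Split-mouth (the more serious case):** with independent randomisation of molars, about half the children give no pair for the planned test.
- **Parallel:** 23 per group is not secured unless the envelopes are a fixed set, but the average power cost is only about 0.7 points. Symptom status differs between arms by 20 points or more in about 16% to 19% of allocations, given the assumed 30% to 50% symptomatic.

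The symptom imbalance is a risk in an unlucky allocation, not a bias in the design. It deserves attention because the factor is known beforehand, is related to the outcome, and is not used in any planned analysis. The parallel figures treat 46 as independent units.

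**What to change.** First state one design in Sections 8, 14, 16 and 20, and say whether 46 counts children or molars.

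- **If split-mouth:** replace simple randomisation of molars with randomisation, within each child, of which side receives Biodentine, the other side receiving MTA. Record symptom status for each molar.
- **If parallel:** use concealed permuted blocks of varying size, with separate lists for symptomatic and asymptomatic molars. Pre-specify a comparison of the materials stratified by, or adjusted for, that status.
- **In either case:** open the numbered envelopes in sequence. A free draw by the child would undo the block order.

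The cost is small. The parallel option needs two lists and two sets of envelopes. Blocks make allocation slightly more predictable for the operator, who assigns patients and is not among those listed as blinded in Section 17. Varying block sizes, and keeping the planned opening of the envelope only after access preparation, limit this. The change has to be made before enrolment. An adjusted analysis could be added later, but missing pairs could not be recovered.
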